16.3 SAMPLE SIZE DETERMINATION AND POWER / ACCRUAL RATE

The sample size was calculated for the primary outcome (average pain intensity over the past 7 days six months after surgery). Assuming that a 2-point change on the 0–10 pain intensity scale constitutes a clinically meaningful difference [74,76], a standard deviation of 2.0 units, a study design with 3 repeated measurements having a compound symmetry covariance matrix, a power of 90%, a two-sided alpha level of 0.05 and a conservative autocorrelation coefficient (rho) of one,

a minimum of 22 patients per comparison group is required. To prevent reduced power because of patient loss to follow-up and to minimize confounding effects, 35 patients per group will be enrolled (35 x 4 groups = 150 patients in total).

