4 PRELIMINARY DATA AND CLINICAL DATA

In a previous study, we have demonstrated that presence of pain before surgery was the best predictor of pain intensity after surgery in Adolescent Idiopathic Scoliosis (AIS) patients undergoing surgery [30]. Pain before surgery was reported by 48% of the cohort (n=50) (Figure 1). We also demonstrated that intensity of pain in the first days after surgery was associated with pain intensity weeks after surgery, thus demonstrating the clinical need to improve preoperative and acute pain management in order to minimize long-term consequences.

Figure 1. Patients reporting preoperative pain had greater postoperative pain intensity levels during the first postoperative 24 hours (POD1, $r=0.47$, $p=0.001$) (A), the second 24 hours (POD2, $r=0.35$, $p=0.025$) (B) and at follow-up appointment (4-6 weeks after surgery, $r=0.50$, $p<0.001$) (C). The pain intensity during POD1 was also predictive of the pain intensity during POD2 ($r=0.74$, $p<0.001$) (D) and at follow-up (6 weeks post-surgery, $r=0.43$, $p=0.005$) (E) (Ferland et al. 2016, PMID: 26852092).

In the same cohort, we also quantified neurotransmitters known to be related to pain. The preoperative plasma levels of norepinephrine metabolite metanephrine concentrations revealed to be associated with the postoperative pain intensity (Figure 3). Although preliminary, these results suggested that preoperative inter-individual differences, could explain postoperative pain trajectories.

[figure not shown]
[figure not shown]

[figure not shown]
Figure 2. Preoperative monoaminergic levels on postoperative pain intensity. The preoperative metanephrine plasmatic levels of AIS patients scheduled for surgery. Patients who reported greater pain intensity at 6 weeks after surgery had higher metanephrine plasmatic levels before surgery (n=50, $P<0.001$) (Ferland et al., manuscript in preparation).

In the largest study to examine longitudinal pediatric pain trajectories after spine surgery, Sieberg et al proposed perioperative trajectories of pain experience may be better explained by changes in the central pain modulation rather than in the surgical stimulus itself (Figure 3).

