16.4 STATISTICAL METHODS

Primary End Point: Average pain intensity over the past 7 days (0–10 numerical rating scale where 0 indicated “no pain” and 10 “worst possible pain”) six weeks and six months after surgery (Dworkin et al., 2005).

Secondary end points: Chronicity of postsurgical pain: Six months after surgery, CPSP will be defined in a dichotomous way (yes/no) as the presence of symptoms 6 months after surgery are reported.

Descriptive statistics (means, SD, medians, n, %) will be calculated in order to present baseline characteristics of the different comparison groups and follow-up measures. To better appreciate the evolution of pain intensity (primary endpoint) during the longitudinal follow-up (baseline to six months after surgery), linear mixed models for repeated measures will be achieved for each of the three comparison schemes described above with the inclusion of the following variables as independent variables to obtain adjusted effects: age, functional outcome score and psychological profile (STAI and PCS scores). This type of analysis is justified by its flexibility in regard to missing data caused by patients lost to follow-up [75] and the possibility to adjust for potential confounders (e.g. patients’ demographics, physical and emotional functioning, clinical characteristics such as medication use or scoliosis parameters). Continuous secondary outcomes will be compared between study groups using similar models. Categorical secondary outcomes such as the presence of chronic postsurgical pain measured 6 months after surgery will be compared between study groups using Chi-square tests. The investigator that will be in charge of the statistical analyses will be blinded to group assignment. As a secondary analysis aiming at understanding the underlying changes over time in QST, pain intensity and catecholamine concentrations will be examined using repeated measures analyses.

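### The 22 per group fits a six-month comparison; Section 16.4 models pain from baseline on and names no tested term, so the 90% power and the conservative label are not tied to the analysis

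*Combined protocol and SAP*

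**What the plan says.** Section 16.3 opens with the target: "The sample size was calculated for the primary outcome (average pain intensity over the past 7 days six months after surgery". The inputs are a 2-point difference, "a standard deviation of 2.0 units", and "a power of 90%, a two-sided alpha level of 0.05". It then adds "a study design with 3 repeated measurements having a compound symmetry covariance matrix" and "a conservative autocorrelation coefficient (rho) of one", and arrives at a minimum of 22 per comparison group, with 35 per group to be enrolled to cover loss to follow-up and confounding. It does not list the three measurement times.

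Sections 16.1 and 16.4 place the primary endpoint at both six weeks and six months. For the analysis, 16.4 says that "during the longitudinal follow-up (baseline to six months after surgery), linear mixed models for repeated measures will be achieved". The adjustment variables it names are age, a functional outcome score, and the STAI and PCS scores. Baseline pain is not among them, and no model term (group, group-by-time or a contrast at one visit) is named as the primary test.

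Section 16.5 lists two comparisons: sub-optimal versus optimal responders within placebo, which is not randomised, and clonidine versus placebo within sub-optimal responders, which is.

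**The concern.** The sample size section describes a repeated-measures design and presents its correlation as a safety margin. The analysis section describes a repeated-measures model that starts at baseline. A reader will take the 90% to apply to that model, but it applies to only some of the tests the model can produce.

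The natural set of three visits is baseline, six weeks and six months. If baseline is one of them, a constant 2-point difference across visits cannot arise in the randomised comparison, since the arms have not yet been treated at baseline. The assumption that makes rho = 1 the cautious choice then fails.

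If the term is instead change from baseline or group-by-time, power falls as rho falls. Rho = 1 would give change a variance of zero, the opposite of caution.

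With the tested term open, the analyst can later choose among terms whose power differs widely on the same data, and the stated 90% cannot be checked against any one of them.

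**Working it through.** **Inputs from 16.3:** difference 2, SD 2.0, two-sided alpha 0.05, power 90%, three measurements, compound symmetry, rho 1, minimum 22 and planned 35 per group. **From Section 10:** 1:1 allocation. **Assumed here, not in the documents:** the three visits are baseline, six weeks and six months, and the true group differences at these visits are 0, 2 and 2. The zero at baseline is justified only for clonidine versus placebo.

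**Step 1: reproduce 22.** For a constant difference averaged over three visits, n = 2 x (1.960 + 1.2816)^2 x 2^2 x [(1 + 2 rho)/3] / 2^2.
- At rho = 1 the bracket is 1, so n = 21.01, rounded up to 22. This is the ordinary two-sample size for a single visit.
- At rho = 0.5 the same formula gives 15, and at rho = 0 it gives 8. For this one type of test, rho = 1 is indeed the cautious value.
- By noncentral t, power at a single visit is 90.0% with 22 per group and 98.5% with 35.

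**Step 2: power of the terms the 16.4 model could supply** (two-sample noncentral t).
- Group effect averaged over three visits: difference (0 + 2 + 2)/3 = 1.333; SD = 2 x sqrt((1 + 2 rho)/3).
- Change from baseline to six months: difference 2; SD = 2 x sqrt(2(1 - rho)).
- Six-month contrast, unadjusted: difference 2; SD = 2, whatever rho is.
- Six-month contrast adjusted for baseline: difference 2; SD = 2 x sqrt(1 - rho^2).

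| Tested term | rho | Power at 22 | Power at 35 |
|---|---|---|---|
| Averaged over three visits | 0 | 96% | above 99% |
| | 0.25 | 86% | 97% |
| | 0.5 | 75% | 92% |
| | 1 | 58% | 79% |
| Change from baseline | 0 | 63% | 83% |
| | 0.25 | 75% | 92% |
| | 0.5 | 90% | 98.5% |
| Six months, unadjusted | any | 90% | 98.5% |
| Six months, adjusted for baseline | 0 | 90% | 98.5% |
| | 0.5 | 96% | above 99% |

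**Step 3: n needed for 90% power** (normal approximation).
- Averaged term: 21.01 x [(1 + 2 rho)/3] x (2/1.333)^2, which is 16, 32 and 48 at rho 0, 0.5 and 1.
- Change from baseline: 42.03 x (1 - rho), which is 43, 32 and 22 at rho 0, 0.25 and 0.5.
- Adjusted six-month contrast: 21.01 x (1 - rho^2), which is never above 21.01, so 22 is enough at any rho.

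**Which rho is plausible?** The nearest figure in the documents is the pilot correlation of 0.50 in Section 4 between pre-operative pain and pain "at follow-up appointment (4-6 weeks after surgery". The text there speaks of the presence of pre-operative pain, so this may not be a correlation between two intensities on the 7-day scale. No six-month value is given, so the results are shown over a range.

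**The case against.** The strongest reply is that nothing in 16.3 is miscalculated. The 22 follows from its inputs, the section says outright that it is sized for six-month pain, and that contrast can be taken from the planned model with 90% power at 22. For a constant difference over visits, rho = 1 is rightly called conservative. All of this stands: there is no arithmetic error in the 22.

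A reader might infer from the table that the trial's true power is 58%. The documents do not support that. The figure needs four things together: a test averaging over baseline, which 16.4 does not name; rho of exactly 1; a 0, 2, 2 effect; and only 22 of 35 patients analysed, a loss of 13/35 = 37%. With all 35 the same case gives 79%. Nor is 58% a floor: if the effect appears only at six months, the averaged term has 19% power at 22 per group with rho 1. These figures show how much depends on the unnamed term; they do not estimate the trial's power.

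Three further limits stand. The set of visits is inferred, and pain is also scored on days 1, 2 and 5. The mean of the two follow-up visits in 16.1 would keep at least 90% power at 22 for any rho, given a 2-point effect at both. The zero-baseline argument does not reach the sub-optimal versus optimal comparison, where groups may differ before surgery.

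What the reply leaves open is the link between the two sections: 16.4 does not say that the six-month contrast is the test. The enrolment of 35 is not spare cover for that gap, because 16.3 already assigns it to loss to follow-up and confounding.

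**Conclusion.** The point holds as a mismatch between sizing and analysis, not as a wrong sample size. The 22 is right for a two-group comparison at six months. The three-measurement and rho wording adds nothing to it and suggests a margin that does not carry over to change from baseline, or to a group effect averaged over visits that include baseline.

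Under SD 2 and effects of 0, 2 and 2, the averaged effect has 96%, 75% and 58% power at 22 per group for rho 0, 0.5 and 1 (above 99%, 92% and 79% at 35). Change from baseline has 63%, 75% and 90% at 22 for rho 0, 0.25 and 0.5 (83%, 92% and 98.5% at 35). The shortfall is therefore conditional on which term is tested and on rho; it disappears if the six-month contrast is the test. The figures for the first two terms rest on the inferred visits and, through the zero at baseline, apply only to clonidine versus placebo.

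**What to change.** In 16.3, delete the three-measurement, compound symmetry and rho wording, leaving 22 per group as the size for the between-group difference at six months.

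In 16.4, name the between-group contrast at six months, adjusted for baseline pain, as the primary test for clonidine versus placebo, in place of any group effect averaged over visits that include baseline. For sub-optimal versus optimal responders, name the six-month contrast as the test; whether to adjust it for baseline pain is a separate choice, because those groups are not randomised.

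The cost is a few sentences in two sections. Baseline pain is already collected (Section 9.1), and no patients, visits or data are added. If the sponsor prefers another term, power should be recomputed for that term over a stated range of rho.

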11.2.4 QST THERMAL FAMILIARIZATION PRE-TEST	32
12 PAIN ASSESSMENT QUESTIONNAIRES	34
12.1 In-Hospital Additional Measures:.....	35
12.1 STUDY PLAN TABLE	35
13. SUBJECT SAFETY	36
13.1 SAFETY AND TOXICITY ASSESSMENT	36
13.2 ADVERSE EVENT AND ADVERSE DRUG REACTION (adr).....	36
13.3 SERIOUS ADVERSE EVENT OR ADVERSE DRUG REACTION	37
13.4 ANTICIPATED ADVERSE DRUG REACTIONS.....	37
13.5 SERIOUS ADVERSE EVENT AND ADVERSE DRUG REACTION REPORTING	39
13.6 NOTIFYING HEALTH CANADA	39
13.7 UNBLINDING PROCEDURE	40
14 DATA HANDLING AND RECORD KEEPING	41
14.1 CONFIDENTIALITY AND SECURITY.....	41
14.2 QUALITY CONTROL AND QUALITY ASSURANCE.....	41
14.3 DATA STORAGE.....	41
14.4 CONFIDENTIALITY AND SECURITY.....	41
14.5 SOURCE DOCUMENTATION.....	42
14.6 RECORD RETENTION	43
15 QUALITY CONTROL AND QUALITY ASSURANCE.....	43
15.1 DATA SAFETY MONITORING BOARD (DSMB)	43
15.2 STUDY MONITORING PLAN	43

16 STATISTICAL CONSIDERATIONS	44
16.1 PRIMARY STUDY ENDPOINTS.....	44
16.2 SECONDARY ENDPOINTS	44
16.3 SAMPLE SIZE DETERMINATION AND POWER / ACCRUAL RATE	44
16.4 STATISTICAL METHODS.....	44
16.5 STRATIFICATION FACTORS.....	45
17 FINANCE.....	45
18 REFERENCES	45

Study Summary

Title	Sensorial and physiological mechanism-based assessments of perioperative pain
Short Title	RCT
Methodology	Randomized-controlled double-blind study
Study Duration	5 years
Study Site(s)	Shriners Hospital for Children Canada
Objectives	The overall goal of this proposal is to determine if quantitative sensory testing (QST) assessing pain modulation can be used as a clinical tool to optimize perioperative pain management. The central hypothesis is that the identification of patient's sensory pain profile allows personalizing therapeutic approaches to improve individualized pain management and thus prevents pain chronicity.
Number of Subjects	150 (approximately 75 for each arm)
Diagnosis and Main Inclusion Criteria	Female patients between 10 and 21 years old with a diagnosis of Adolescent Idiopathic Scoliosis (AIS) and no concomitant diseases, who are scheduled for scoliosis surgery at the Shriners Hospital, will be invited to participate in the study.
Study Product, Dose, Route, Regimen	Arm 1 - Intrathecal Clonidine after to surgery & PO Clonidine for 5 days post-op
Duration of administration	Day of surgery and 5 days post-operatively.
Reference therapy	Arm 2 - Intrathecal Morphine after to surgery & PO Placebo for 5 days post-op

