7 SUBJECT SELECTION

This study aims to recruit 150 female patients, with approximately 75 per group. The scientific rational to exclude male patients is straight forward. Knowing that gender can influence the quantitative sensory testing – knowing that gender can also affect pharmacokinetics, we felt prudent to minimize our variables to ensure our N will be able to show the expected outcome. If and once our hypothesis has been shown, then the protocol will be amended to include males to see if clonidine also improves acute chronic pain management.

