8 STUDY DESIGN/PROCEDURES

8.1 GENERAL DESIGN

This study is a randomized-controlled double-blind study. All consecutive female patients who come to the Shriners Hospital for Children – Canada, and who meet the Inclusion/exclusion criteria will be invited to participate in the study throughout the study's specified recruitment period to avoid selection bias.

Subjects will be expected to participate for 6 months. Subjects will be assessed for eligibility, consented and enrolled if they meet all criteria. They will undergo a baseline visit prior to surgery. CPM testing results will determine the subjects to be in one of two arms – 1) Sub-optimal endogenous inhibitory response or 2) Optimal endogenous inhibitory response. The subjects in each of these two groups will be randomized to either be treated with Clonidine arm or the placebo arm. Subjects will be followed in-hospital, and at 6 weeks and 6 months.

All clinicians and researchers involved in the recruitment, consent, data collection, experimental procedures and data analysis will remain blinded to study group allocation for the duration of the study. Blinding will be maintained until the end of statistical analysis, unless un-blinding is required. Although the study will be conducted at the Shriners Hospital for Children – Canada, including analysis of all specimens, the Pharmacy of the McGill University Health Centre will manage the randomization, blinding of medication/placebo as well as the distribution of the medication/placebo on the day of surgery and for 5 days post-operatively.

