9 STUDY INFORMATION

9.1 BASELINE VISIT

The expected duration for the patient's participation in the research is 6 months and will consist of a baseline visit, In-hospital visit, 6 week post-op visit and a 6 month post-op visit.

At the baseline visit, the subject will be expected to complete the following:

- ✓ Pain intensity rating (self-reported) (Wong Baker Faces Pain Scale)

- ✓ Medical History Interview (Patient History Collection Form)
- ✓ Approximately 10 mL of blood will be drawn and blood pressure will be taken
- ✓ Quantitative Sensory Testing (QST = MDT/PPT/CPM tests)

The subject will be expected to fill out the following questionnaires:

- ✓ Pain numerical rating scale for children (Baseline - 4 questions)
- ✓ State-Trait Anxiety Inventory (STAI-C)
- ✓ Pain Catastrophizing Scale (PCS-C)
- ✓ Functional Disability Index (FDI)
- ✓ Revised Children Anxiety and Depression Scale (RCADS)
- ✓ Pittsburg Sleep Quality Index (PSQI)
- ✓ Neuropathic Pain Questionnaire (DN4)
- ✓ Tampa Scale for Kinesiophobia (TSK)
- ✓ Scoliosis Research Society (SRS-30)
- ✓ Adolescent Pediatric Pain Tool (APPT)

The visit should take approximately 1 hour

Once the subject's CPM results from the baseline visit have been assessed, the subject will be categorized into one of two arms: 1) Sub-optimal endogenous inhibitory response or 2) Optimal endogenous inhibitory response. The sub-optimal group will then be randomized to either Clonidine or the placebo, and the optimal group will be also randomized to either Clonidine or the placebo.

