10 STUDY AGENT INFORMATION

QST results will show that subjects either have an optimal or a sub-optimal response. The subjects who fall into the optimal category will be randomized to either Clonidine or placebo and the subjects who fall into the sub-optimal category will also be randomized into either Clonidine or placebo. The hospital pharmacy will do 1:1 randomization using online software.

Randomization and blinding of the medications and placebo will be performed by the hospital pharmacy. The pharmacy will be sent the list of patients participating in the study. They will maintain the trial treatment randomization codes, and procedures for breaking codes will be also carried out by the pharmacy.

For each study patient, the physician will supply the pharmacy with a prescription ordering medication for the Clonidine arm OR the placebo arm according to what the patient is randomized to. The pharmacy will prepare the appropriate medication kits, according to the randomization assignment, either containing vials of Clonidine or intrathecal morphine. For the day of surgery, the pharmacy will prepare a blinded kit containing the medication, preparation materials and instructions. Either the evening before, or the morning of the surgery, the research assistant will go to the pharmacy and pick up the blinded study medication kit and deliver it to the OR. The respiratory therapist will prepare the medication contained in the kit in the operation room just prior to surgery and then give it to the anesthesiologist who will administer it to the patient.

The 5 days of post-operative medication, either Clonidine or placebo, according to patient's randomization prescription, will be dispensed daily from the hospital's pharmacy, along with their regular routine medications.

As per Standard of care, concomitant therapy will be provided for pain, anti-nausea and for any other reasons that may occur. These therapies will be given in addition to the study medications.

All medications given to the patient will be noted in the patient's medical chart by the nurse. The patient's medical chart will then be verified daily by a research assistant for study drug compliance. In the event of non-compliance, a Note File will be added to the patient's study file listing the reasons why, and the action taken and filed in the patient's study file. Providing patients wish to remain in the study, they will not be discontinued from the study for non-compliant medication intake.

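### Section 16.3 multiplies 35 patients by 4 groups and gets 150; the product is 140, so the per-group size and the total enrolment disagree by 10 patients

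*Combined protocol and SAP*

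**What the plan says.** Section 16.3 derives the trial's size in two steps. On its assumptions (a 2-point difference, a standard deviation of 2.0, 90% power, two-sided alpha 0.05, three measurements with a correlation of one) it concludes that "a minimum of 22 patients per comparison group is required". It then raises that number, giving as the reason "To prevent reduced power because of patient loss to follow-up and to minimize confounding effects", and states the result: "35 patients per group will be enrolled (35 x 4 groups = 150 patients in total".

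Two other places give the size. The Study Summary has "150 (approximately 75 for each arm". Section 7 has "This study aims to recruit 150 female patients, with approximately 75 per group". The number of groups is settled in three more. Section 8.1, having split patients into sub-optimal and optimal CPM responders, says "The subjects in each of these two groups will be randomized to either be treated with Clonidine arm or the placebo arm". Section 9.1 says the same of the first category, "The sub-optimal group will then be randomized to either Clonidine or the placebo", and goes on to the second. Section 10 gives the ratio: "The hospital pharmacy will do 1:1 randomization using online software". That makes four cells.

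**The concern.** The multiplication in section 16.3 is wrong on its face, and its two factors lead to a different trial from the one described elsewhere. A reader who follows the 35 arrives at 140 patients and 70 per arm. A reader who follows the total arrives at 150 and 75 per arm, in line with the Study Summary and section 7, but then the per-group figure is not 35.

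Section 16.3 is the only place where the number of patients is justified. If its last line does not add up, the total in use has no stated derivation. The total also fixes when recruitment ends and when the second monitoring visit in section 15.2 falls due, since that visit is tied to half the patients having been recruited: patient 70 or patient 75.

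**Working it through.** **Inputs.** From section 16.3: difference 2, SD 2.0, two-sided alpha 0.05, power 90%, 3 measurements under compound symmetry with rho = 1, minimum 22 per group, 35 enrolled per group, 4 groups, total 150. From the Study Summary and section 7: total 150, about 75 per arm. From sections 8.1, 9.1 and 10: two CPM categories, each randomised 1:1 between two treatments.

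**Step 1: the plan's minimum.** With m = 3 and rho = 1 the repeated-measures variance factor is (1 + (m − 1) × rho)/m = (1 + 2)/3 = 1, so the repeated measurements bring no gain. The normal-approximation formula is

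n per group = 2 × (z for alpha + z for power)² × (SD/difference)² = 2 × (1.96 + 1.2816)² × (2/2)² = 21.01, rounded up to 22.

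The stated 22 reproduces. The exact two-sample t-test at 22 per group has power 0.8997, that is, 90%.

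**Step 2: the total.**

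- 35 × 4 = 140; the plan states 150, a difference of 10.
- 10/150 = 6.7% of the stated total.
- 140/2 = 70 per arm; 150/2 = 75 per arm, a difference of 5.
- 150/4 = 37.5 per cell on average, 2.5 more than 35.
- 37.5 is not a whole number; equal whole cells would give 4 × 37 = 148 or 4 × 38 = 152.

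**Step 3: could an allowance for loss explain it?** With n/(1 − d), going from 22 to 35 implies d = 1 − 22/35 = 37.1%, and going from 22 to 37.5 implies d = 1 − 22/37.5 = 41.3%. The plan states neither rate. Its reasons for inflation are attached to the 35, and no second allowance is given.

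**Step 4: effect on power.** Two-sample t-test, standardised difference 2/2 = 1, two-sided 0.05, equal cells, no loss:

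| Per cell | Power |
|---|---|
| 22 | 0.8997 |
| 35 | 0.9848 |
| 37.5 (average) | 0.9896 |

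**Step 5: sensitivity to the CPM split.** The plan sets no quota by CPM category, so cell sizes depend on how consecutive patients divide. The share in the smaller category is not given; the values below are assumptions. Smaller cell = total × share/2.

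| Assumed share | Total 140 | Total 150 |
|---|---|---|
| 50% | 35 | 37.5 |
| 40% | 28 | 30 |
| 30% | 21 | 22.5 |

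The smaller cells reach 22 only if the share is at least 44/140 = 31.4% or 44/150 = 29.3%. Loss to follow-up would reduce them further: a cell of 28 falls below 22 once loss exceeds 1 − 22/28 = 21.4%.

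**The case against.** The strongest reply is that the target is not really in doubt. Every total written in the documents is 150, in three places, and two of those add about 75 per arm. Neither 140 nor 70 per arm is written anywhere; both are derived from the 35. Staff would in all likelihood recruit to 150, and the slip is confined to one parenthesis. This stands as far as it goes, and it suggests 150 is the figure in use. It does not show how 150 was obtained, and the same sentence presents 35 as the number to be enrolled in each group. The word for approximately in the Study Summary and section 7 qualifies the 75, not the product.

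The second reply is that nothing depends on the error: the minimum of 22, the design, the allocation and the analysis are unchanged, and power is high at either size. That is right for equal cells without loss. It is not a general assurance, since a 30% smaller category would put cells at 21 or 22.5 before any loss. But that weakness comes from the unset CPM split, and the choice between 140 and 150 does little to remove it.

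A third reply is that calling the per-cell number an average raises a separate matter, because section 16.3 reads as if 35 were fixed for each group. It is separate from the multiplication, but a total of 150 cannot be reported as a per-cell figure in any other way unless quotas are set.

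**Conclusion.** The point holds. The product in section 16.3 is wrong as written: 35 × 4 is 140, and the stated 150 corresponds to an average of 37.5 per cell. The discrepancy is 10 patients in total, 5 per arm and 2.5 per cell on average. The documents do not show whether the per-group figure or the total was intended.

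The statistical consequence is negligible. The required minimum of 22 is correct, and power for the stated comparison is 98.5% at 35 per cell and 99.0% at 37.5, against a planned 90%. Those powers assume equal cells, no loss to follow-up and the plan's own difference and SD. The matter should be fixed because a sample size is a figure the trial relies on and its only justification contradicts itself; no conclusion of the trial is put at risk by it.

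**What to change.** Correct section 16.3 so that the per-group size and the total agree, in one of two ways:

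- keep 35 per group and state a total of 140, about 70 per arm; or
- keep 150 in total, about 75 per arm, and state an average of 37.5 per cell, with the reason for going beyond 35.

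In either case use the same figures in the Study Summary, section 7 and section 16.3, and describe the per-cell number as an average, because no quota by CPM category is set.

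The cost is wording only. Keeping 150 changes one sentence in section 16.3; choosing 140 also changes the Study Summary and section 7. The minimum of 22, the allocation and the analysis are not affected.
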